9.1.3. Appropriateness of Assessments

There is no universally accepted measure of medication adherence, but following recommendations in the scientific literature, we will measure adherence using multiple assessments that seek to capture various facets of medication use as described in section 9.1.1. These self-report measures are appropriate given the study design. Since one or two interviews will be conducted via phone, we would be unable to use assessments that require in-person administration or orientation (i.e. MeMS caps; pill counts). As

patients are enrolled in the study for three months, pharmacy fill data would also not provide a meaningful measure of adherence (beyond initial fill). Finally, as many of the medications targeted in this study are injectables, conducting a pill count would be unsuitable.

9.2. Adverse Events

Adverse Drug Events (ADE) will be assessed using a questionnaire administered by the RA during the 3 month follow-up phone call. If the patient states that they have experienced an ADE and provides any details, the RA will fill out an adverse event form to send to Eli Lilly. [name] at Northwestern (or another clinic contact in the event of her absence) or the Access Community Health Network clinical liaison will also be informed if the patient answers as described above and/or reports they have not contacted their doctor. They will use clinical expertise to determine appropriate next steps. This protocol will comply with our requirements that investigators and other study personnel are requested to report any suspected adverse reactions with any drug to the appropriate party (for example, regulators or the marketing authorization holder) as they would in normal practice as required by applicable laws, regulations, and practices.

9.2.1. Complaint Handling

Lilly collects product complaints on investigational products and drug delivery systems used in clinical studies in order to ensure the safety of study patients, monitor quality, and to facilitate process and product improvements.

Patients will be instructed to contact the investigator as soon as possible if he or she has a complaint or problem with the investigational intervention so that the situation can be assessed.

9.3. Treatment of Overdose

Not applicable.

9.4. Safety

Not applicable.

9.4.1. Electrocardiograms

Not applicable.

9.4.2. *Vital Signs*

Not applicable.

9.4.3. Laboratory Tests

Not applicable.

9.4.4. *Other Tests*

Not applicable.

9.4.5. Safety Monitoring

Not applicable.

9.5. Pharmacokinetics

Not applicable.

9.6. Pharmacodynamics

Not applicable.

9.7. Pharmacogenomics OR Genetics

Not applicable.

9.7.1. [Whole Blood and/or Saliva] Sample[s] for Pharmacogenetic Research

Not applicable.

9.8. Biomarkers and specify other analyses

Not applicable.

9.8.1. Samples for Immunogenicity Research

Not applicable.

9.9. Health Economics [OR] Medical Resource Utilization and Health Economics

Health Economics and Medical Resource Utilization parameters were not evaluated in this study.

10. Statistical Considerations

10.1. Sample Size Determination

The sample size for this pragmatic study was based on comparisons of the primary outcome of medication knowledge between the two arms (i.e., usual care vs EMC²) at the T2 interview. We expect patients in the usual care arm to score an average of 55.6% correct responses (SD=28.4) based on a previous study that tested comprehension of the FDA standard Med Guides to those to be used in this study(9). Enrolling 330 patients and estimating 90% retention at the T2 interview (N=300, 150 per arm, 6 per provider), we will have 80% power to detect a minimum difference of 9.4% between the EMC² and the usual care arm assuming a Type I error of 5% (improving from 55.6% to 65.0% or greater). An intra-class correlation coefficient (ICC) of 0.001 was used; we expect clustering of physicians to have minimal influence on outcomes. However, even if the ICC were higher (i.e. 0.01) we could still detect a difference as small as 9.6%.

With the sample size set by the primary outcome, we also report minimum detectable differences for medication adherence measures. We estimate 65% of the usual care arm to demonstrate proper use of their medications based on prior studies(1, 18). With similar assumptions described above, a sample of 300 participants would enable us to detect a minimum absolute difference of 14.4% between arms with an ICC of 0.001 and 14.7% with an ICC of 0.01. We expect participants in the usual care arm to score an average of 27.5 (SD=7.2) on the ASK-12 based on validation studies(15). Retaining 300 participants (150 per arm, 6 per provider) at the T2 follow-up interview we will have 80% power to detect a minimum difference of 2.4 between the EMC² and the usual care arm (improving from 27.5 to 25.1 or less) using an ICC of 0.001 and a difference of 2.5 (improving from 27.5 to 25.0 or less) and with an ICC of 0.10. While no cut-off indicating non-adherence is provided, the goal would be for patients to score below 22.5, the average score in patients who took medications exactly as directed in the ASK-12 validation studies(15). We could detect differences smaller than this with the proposed sample size. In addition, differences in subscale scores of 1.3 for behavior, 0.9 for health beliefs, and 1.0 for inconvenience/forgetfulness could be detected between arms assuming mean scores of 10.5 (SD=3.8), 8.1 (SD=2.7), and 8.9 (SD=3.0), respectively, in the usual care arm.

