7.3. Method of Treatment Assignment

As the EMC² Strategy includes changes to healthcare delivery, the intervention itself is diffuse and individual patient randomization is not feasible. Therefore, randomization will occur at the provider (specifically, prescriber) level (N= ~50 eligible clinicians). Specifically, prescribers will be randomized to study arm (EMC² Strategy or usual care) prior to the initiation of the study. As patients are enrolled in the study, they will be automatically assigned to either intervention or usual care arms based upon the initial assignment of their physician. This specific strategy of "turning on" an EHR intervention with physician or clinic level randomization has been previously approved by the IRB at Northwestern University for three other AHRQ funded grants [P01HS021141-01, 1U19HS021093-01 & 1R18HS017220-01]. To optimize the likelihood of obtaining similar populations in each study arm, physicians will be placed into 4 strata based on workload (full time vs. part time) and site and randomly assigned to one of the two arms with an equal number assigned to each arm within each strata.

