10.3. Statistical Analyses

10.3.1. General Statistical Considerations

We will perform analyses to address each of the aims using SAS v9.4 (Cary, NC).

The proposed trial uses a cluster-randomized design where the prescribing physician is the unit of randomization. We will randomize providers (i.e. attendings and fellows) to one of two intervention arms (usual care, EMC2). To optimize the likelihood of obtaining similar populations in each, providers will be placed into strata based on their

roles (attending, fellow) and historical volume of study medications dispensed (high, medium, low) for attendings. Providers from each strata will be randomized and identities will be revealed after randomization is complete. Patients enrolling in the study are assigned to the study arm of the provider signing their prescription within the EHR.

Given the brief follow-up period, we anticipate ~90% retention at T2 interview. These estimates result in 330 patients recruited with an anticipated 300 patients (150 per arm) available for primary data analysis.

Effectiveness analyses will be conducted on the full analysis set. This set includes all data from all randomized patients completing the outcomes of interest according to the treatment the patients were assigned.

All tests of treatment effects will be conducted at a 2-sided alpha level of 0.05, unless otherwise stated.

Any change to the data analysis methods described in the protocol will require an amendment ONLY if it changes a principal feature of the protocol. Any other change to the data analysis methods described in the protocol, and the justification for making the change, will be described in the clinical study report (CSR). Additional exploratory analyses of the data will be conducted as deemed appropriate.

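### The ASK-12 detectable difference of 2.5 at an ICC of 0.10 does not follow from the section's own inputs, which give 2.9 at 0.10 and 2.4 at 0.01

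*Combined protocol and SAP*

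**What the plan says.** Section 10.1 (Sample Size Determination) fixes the sample size on medication knowledge and then reports what the same sample can detect on the adherence measures. Each of three outcomes gets a detectable difference at an ICC of 0.001 and at one higher ICC:

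- **Knowledge:** 9.4 points at 0.001, and then "However, even if the ICC were higher (i.e. 0.01) we could still detect a difference as small as 9.6" percent.
- **Proper use:** "14.4% between arms with an ICC of 0.001 and 14.7% with an ICC of 0.01".
- **ASK-12:** 2.4 points (27.5 to 25.1) for the first pair. The sentence then continues "using an ICC of 0.001 and a difference of 2.5 (improving from 27.5 to 25.0 or less) and with an ICC of 0.10".

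The ASK-12 statement rests on "Retaining 300 participants (150 per arm, 6 per provider) at the T2 follow-up interview we will have 80% power", with a usual-care mean of 27.5 and an SD of 7.2. The section also states that "differences in subscale scores of 1.3 for behavior, 0.9 for health beliefs, and 1.0 for inconvenience/forgetfulness could be detected between arms", without naming an ICC for the subscales.

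**The concern.** The higher ICC for ASK-12 is ten times the one used for the other two outcomes, yet the detectable difference barely moves, from 2.4 to 2.5. With 6 patients per provider, an ICC of 0.10 inflates the variance by half, which should widen the detectable difference by about a fifth.

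In a trial randomized by prescriber, these paired figures exist to show how well power holds up if clustering is stronger than assumed. As printed, the protocol says that ASK-12 power survives fairly strong clustering almost intact. If 0.10 was meant, that assurance is wrong. If 0.01 was meant, a reader is misled about which value was checked.

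**Working it through.** **Inputs**

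- SD 7.2; 150 retained per arm; 6 per provider; 80% power (Section 10.1). The 90% retention is already applied.
- Type I error of 5% (Section 10.1), two-sided: "All tests of treatment effects will be conducted at a 2-sided alpha level of 0.05, unless otherwise stated" (Section 10.3.1).
- About 50 prescribers: "randomization will occur at the provider (specifically, prescriber) level (N= ~50 eligible clinicians" (Section 7.3). This agrees with 300/6 = 50 and gives 50 − 2 = 48 degrees of freedom for a cluster-level comparison.

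**Formulas**

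Design effect: DE = 1 + (6 − 1) × ICC.

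Standard error of the difference: SE = SD × √(2 × DE / 150).

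Detectable difference: MDD = k × SE. For two-sided 5% and 80% power, k = 1.960 + 0.842 = 2.802 (normal), 2.811 (noncentral t, 298 df) or 2.859 (noncentral t, 48 df).

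**Step 1: reproduce the plan's other figures (t, 48 df)**

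| Outcome (SD) | ICC | Computed | Printed |
|---|---|---|---|
| Knowledge (28.4) | 0.001 | 9.40 | 9.4 |
| Knowledge (28.4) | 0.01 | 9.61 | 9.6 |
| ASK-12 (7.2) | 0.001 | 2.38 | 2.4 |
| Behavior (3.8) | 0.001 | 1.26 | 1.3 |
| Health beliefs (2.7) | 0.001 | 0.89 | 0.9 |
| Inconvenience/forgetfulness (3.0) | 0.001 | 0.99 | 1.0 |

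The normal version gives 9.21 and 9.41 for knowledge, so it serves here only as a bound. Proper use, from 65% with unpooled variance, gives 14.6% and 14.9% with 48 df against the printed 14.4% and 14.7%; the 298-df version matches those two. No single version matches every printed figure, so all three are shown below.

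**Step 2: the disputed pair**

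At ICC 0.10, DE = 1 + 5 × 0.10 = 1.50, and SE = 7.2 × √(2 × 1.50 / 150) = 7.2 × 0.1414 = 1.018. At ICC 0.01, DE = 1.05 and SE = 7.2 × √(2 × 1.05 / 150) = 0.852.

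| | Normal | t, 298 df | t, 48 df |
|---|---|---|---|
| MDD at ICC 0.01 | 2.39 | 2.39 | 2.44 |
| MDD at ICC 0.10 | 2.85 | 2.86 | 2.91 |
| Power at 2.5, ICC 0.01 | 84% | 83% | 82% |
| Power at 2.5, ICC 0.10 | 69% | 69% | 67% |
| ICC at which MDD = 2.5 | 0.030 | 0.029 | 0.021 |

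By the normal approximation, 2.5 at ICC 0.10 would need about 197 per arm, against the 150 planned.

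**Step 3: a check that does not depend on the approximation**

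Within any one version, k, the SD and n cancel from the ratio of two detectable differences. From ICC 0.001 to 0.10 the ratio must be √(1.50 / 1.005) = 1.22. The printed ratio is 2.5 / 2.4 = 1.04.

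**Step 4: can another reading rescue it?**

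- *Rounding.* Values from 2.45 to 2.55 correspond to ICCs of about 0.012 to 0.040 across the three versions, never 0.10.
- *No attrition.* With 165 per arm (6.6 per provider) the result at 0.10 is 2.77 to 2.83.
- *One-sided test.* By the normal approximation this gives 2.53 at 0.10, but then 2.07 at 0.001 instead of the printed 2.4, and it contradicts Section 10.3.1.

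**The case against.** The strongest case accepts the arithmetic and disputes its reading and weight.

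- **Under the favoured reading nothing is overstated.** If 0.01 was meant, power at 2.5 is 82% to 84%, so the printed difference is slightly conservative and only a digit of the ICC is wrong. This stands, but the documents do not settle which reading applies.
- **A slip in the ICC alone does not explain the pair.** At 0.01 the result rounds to 2.4; 2.5 appears only if 2.44 is rounded up, or if the already rounded 2.4 is scaled (2.4 × √(1.05 / 1.005) = 2.45). This also stands: under that reading both figures need changing. It is a reason to check both, not to leave the sentence.
- **The subscales are weak evidence for 0.01.** With 48 df they would be 1.54, 1.09 and 1.21 at ICC 0.10, so the printed 1.3, 0.9 and 1.0 were not computed there. They could simply be base-case values at 0.001, however, which says nothing about the second ICC. The inference to 0.01 rests mainly on the parallel with knowledge and proper use.
- **The method behind the section is not fully established**, because proper use fits a different version best. This is true, but no version tried gives 2.5 at ICC 0.10, and the ratio check does not need one.
- **The consequence is small.** Agreed: the sample size was set on knowledge, and ASK-12 is one of four adherence measures in Section 9.1.2.

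**Conclusion.** The concern holds. The printed pair is inconsistent with the section's own inputs under either reading: 2.5 should be about 2.9 if the ICC is 0.10, and 2.4 if it is 0.01. Taken literally, the statement promises 80% power where the design gives 67% to 69%.

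This assumes equal clusters of 6, the usual design effect for comparing two means, a common SD of 7.2 in both arms and a two-sided 5% test. That 0.01 was intended is the likelier explanation, not an established fact.

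The error affects one power statement for a secondary measure. The sample size, the primary-outcome figures and the planned analysis are untouched.

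**What to change.** Confirm from the original calculation which ICC was used, then correct the one sentence in Section 10.1 to one of the following:

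- ICC 0.01: difference 2.4 (27.5 to 25.1 or less). The figure becomes slightly more favourable and, to one decimal, equals the one at 0.001.
- ICC 0.10: difference 2.9 (27.5 to 24.6 or less). The figure becomes less favourable.

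Only if 0.10 is confirmed as a plausible ICC, report the other two outcomes at that value as well, so that all three rest on the same clustering range: about 11.5 points for knowledge (t, 48 df) and about 17 percentage points for proper use (17.1 normal to 17.4 t, unpooled variance).

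The cost is a text correction, with no change to enrolment, sample size or analysis.

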10.2. Populations for Analyses

For purposes of analysis, the following populations are defined in table 5.

Table 5 shows study population.

Population	Description
Enrolled	All patients who provide written consent
Randomized	Since this is a provider-randomized study, patients who are enrolled are automatically randomized.
Evaluable	Patients who had no post randomization efficacy measure for the parameter being analyzed will be excluded. Patients will be included in the treatment group they were randomized to regardless of whether the treatment is received as planned.

10.3. Statistical Analyses

10.3.1. General Statistical Considerations

We will perform analyses to address each of the aims using SAS v9.4 (Cary, NC).

The proposed trial uses a cluster-randomized design where the prescribing physician is the unit of randomization. We will randomize providers (i.e. attendings and fellows) to one of two intervention arms (usual care, EMC2). To optimize the likelihood of obtaining similar populations in each, providers will be placed into strata based on their

roles (attending, fellow) and historical volume of study medications dispensed (high, medium, low) for attendings. Providers from each strata will be randomized and identities will be revealed after randomization is complete. Patients enrolling in the study are assigned to the study arm of the provider signing their prescription within the EHR.

Given the brief follow-up period, we anticipate ~90% retention at T2 interview. These estimates result in 330 patients recruited with an anticipated 300 patients (150 per arm) available for primary data analysis.

Effectiveness analyses will be conducted on the full analysis set. This set includes all data from all randomized patients completing the outcomes of interest according to the treatment the patients were assigned.

All tests of treatment effects will be conducted at a 2-sided alpha level of 0.05, unless otherwise stated.

Any change to the data analysis methods described in the protocol will require an amendment ONLY if it changes a principal feature of the protocol. Any other change to the data analysis methods described in the protocol, and the justification for making the change, will be described in the clinical study report (CSR). Additional exploratory analyses of the data will be conducted as deemed appropriate.

10.3.2. Treatment Group Comparability

10.3.2.1. Patient Disposition

A detailed description of patient disposition will be provided at the end of the study.

10.3.2.2. Patient Characteristics

T1 assessment will include socio-demographics, social support, and health status, including number of comorbidities. We will also probe for medication concerns (i.e. about costs, side effects, risks) for patients who do not fill or are not taking their medicine.

Health Literacy. We will assess health literacy via the Newest Vital sign or three validated screening questions that assess health literacy skills.

Patient Motivation. The Consumer Health Activation Index (CHAI) assesses patients' 'activation' or motivation to participate in healthcare decisions and actions.

T1 patient characteristics will be compared by arm using t-tests and χ 2 tests, as appropriate. Any significant differences (p < .05) across study arms will be entered as covariates in models described below.

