At all study sites, a research coordinator (RC) will log in to EPIC to look for an alert if a patient received a new prescription or a dose change for one of the study medications at the study clinic. However, we anticipate that mostly patients with a new prescription will be recruited due to the design of the intervention within EPIC. Alerts in EPIC will only be activated for patients that have not opted out of research. RC will then review the EHR to confirm new or changed prescription and patient portal status. Recruitment will be done by the RC via telephone. Patients will be called via telephone within 1-14 days after their index clinic visit. If they are interested in participating or learning more about the study, the RC will obtain verbal permission to ask the patient a brief series of questions to determine eligibility. If eligible, the RC will schedule a time to complete the T1 interview in person and obtain written consent. If an in person interview is not able to be completed due to COVID-19 institutional policy, the RC will schedule a time to complete the T1 interview over the phone. If all T1 questions cannot be completed in person, they will be completed over the phone.

Table 3 shows patient payment.

Patient Payment:

Research Interview	Payment	Form of Payment
		Cash at close of interview for in person interview OR
T1	\$ 30	Money Order or PNC Visa gift card for telephone interview

T2 S 40 Money order or PNC Visa Gift Card of interview	d sent at close
--	-----------------

Research Coordinator Training. The project lead will lead sessions to orient the research staff to the surveys and study protocols (e.g., interview process, use of laptop PCs, data security). All interviewers will be required to demonstrate competence in survey administration. All RCs have completed human subjects training (CITI) and intensive training from Drs. [name] and [name] in interview protocols and safe data transfer.

Clinic Orientation. Within 1-2 weeks to the launch of the EMC² Strategy at the clinic, Drs. [name], [name], and/or [name] for Northwestern OR [name] for ACCESS Community Health Network will describe the study and what to expect over the upcoming several months to clinic providers and staff. Additional meetings may be held with staff responsible for following up with patients. We anticipate little orientation will be needed as most these sites participated in Phase I.

Study Timelines:

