An individual patient will be involved in the study for a total of up to 3 months. They will complete a screener enrollment interview, a T1 in person or phone interview as soon as possible following the screener, and a final T2 interview on the phone at 3 months.

[figure not shown]
We anticipate that patient enrollment will actively take place until Q2, 2020.

Our proposed/anticipated study timeline is below.

Table 4 shows study measures and outcomes.

			Inter	view			
Variable	Instrument(s) or Measure(s)		T1			T2	EHR Reviev
Covariates		_					
Socio-demographics	Age, sex, race/ethnicity, education, income, insurance/work status, living situation	Summary	•				
Baseline Health Status	Self-reported overall health/chronic conditions	ung	•				
Health Literacy	Chew		•				
Social Support	Tangible social support scale, marital status	Med	•	Week	month		
Patient Activation	Consumer Health Activation Index (CHAI)		•	Ve.	0		
Effectiveness Outcomes		and		7	Е		
Medication Knowledge	Dosage, storage, indication, risks and benefits, side-effects		•		Ξ	•	
Medication Adherence	Self report fill and time to fill	ing	•	ij	ire	•	
	Proper use	sel	•	Ĕ	na	•	
	ASK-12	Ë	•	ō	ou	•	
Fidelity Outcomes		counseling,		Questionnaire-	Questionnaire		
Provider Counseling	Receipt of provider counseling (yes/no)		•	ne	ne		
Qualify of Provider Counseling	CAHPS- communication about medicines	RX	•	g			
Receipt of Materials	Receipt of Med Guide (yes/no)	Ă,	•	rta	tal		
Perceived Helpfulness	How helpful was intervention? (1 to 10 scale)	BPA,	•	Portal	Portal		
Pharmacy Counseling	Receipt of pharmacy counseling (yes/no)		•	-	а.	•*	
Qualify of Pharmacy Counseling	CAHPS- communication about medicines	Visit-	•	1		•*	
Receipt of Portal Email	Completion of portal assessment (yes/no)					•	
	How helpful was intervention? (1 to 10 scale)	Clinic				•	
Clinic Staff Follow-Up Counseling	Receipt of counseling (yes/no)	C				•	
Quality of Clinic Staff Counseling	Self-reported clinic follow-up					•	
Frequency of Clinic Follow-Up	EHR Review of clinic contact with patient			1			•

Figure.1 Illustrates the study design

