5.2. Number of Patients

Patients will be screened to achieve 300 randomized and 300 evaluable patients for an estimated total of 150 evaluable patients per treatment group. Approximately 10 providers will recruited for study feedback. To address potential retention loss (estimate 90% retention), we will target 330 patients to be recruited and consented to the study, completing the baseline assessment.

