7.1. Treatments Administered

This pragmatic study involves a comparison of intervention administered with standard of care in routine care.

Study Arms.

Usual Care: For this study, current usual care includes 1) variable provider counseling without any EHR notifications or counseling support; 2) variable distribution of print medication information materials, including FDA Medication Guides in clinics and variable distribution in pharmacies; and 3) limited or variable active surveillance of medication use post-visits.

Intervention: EMC² Strategy: There are several components that will be embedded into the workflow via EHR/patient portal platforms, mostly automating their implementation. Following patient movement through a provider visit, the following 6 activities will occur:

- 1. *Physician Medication Alert:* If a prescribing physician attempts to place a new order or change to an existing study medication prescription, an EHR-generated alert will notify the provider that the medication requires patient counseling. Physicians can opt to ignore this alert.
- 2. *Provider Counseling Support:* Content from the 1-page, Med Guide Summary will appear on the screen, if selected by the provider, to orient and inform provider-patient discussion.
- 3. Automated Delivery of Med Guide + Summary: When patients leave an encounter, the medication order in Epic will automatically cue printing of both the 1-page, health literate Med Guide Summary for study medications and a full Med Guide, if applicable (latter is required by FDA for certain medications only, the former designed to enhance comprehension). If the medication was ordered during a telemedicine encounter, the Med Guide Summary will automatically populate in the patient portal.
- 4. Follow-Up Portal Questionnaire: Within 1 week post-visit, patients will receive an automated email prompting them to log on to the patient portal. Patients' will be asked to fill out a short set of questions related to medication adherence, and other medication-related concerns (i.e. cost, side effects). If patients have not completed the questionnaire within 2 days, another email reminder will be sent. The information submitted back by the patient will be stored in the EHR.

Content in question form and corresponding responses for the portal questionnaire will be revised from prior evaluation scripts and written by Drs. [name], [name], [name], and [name].

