7.4. Blinding

This is an open-label pragmatic study. As with most behavioral interventions, it will not be possible to fully blind researchers, healthcare providers, and study patients to intervention vs. usual care assignments. However, we have purposefully designed our trial to prevent certain threats to contamination between study arms. Patients will be told they will receive one of two models of care. While they will not be deliberately made aware of the approach not received, we do recognize that there is an unavoidable risk of patients learning from other patients involved in the study.

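### Significance tests on T1 measures, taken after the index visit, decide which covariates enter the primary model, and CHAI is one of the candidates

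*Combined protocol and SAP*

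**What the plan says.** **Covariate rule.** Section 10.3.2.2 tests T1 characteristics by arm with t-tests and chi-square tests. It then states: "Any significant differences (p < .05) across study arms will be entered as covariates in models described below". CHAI is described in that section as a measure of motivation, and Table 4 in section 5.1 lists "Consumer Health Activation Index (CHAI)" among the covariates, collected at T1 only. No T1 variable is exempted on the ground that the intervention could have changed it.

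**Second route.** Section 10.3.3.1 examines how potential confounders relate to knowledge and adds fixed effects for those noted, with no threshold. Its list does not name CHAI.

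**Order of events.**
- Prescribers are randomized before the study starts. On patients, section 7.3 says: "As patients are enrolled in the study, they will be automatically assigned to either intervention or usual care arms".
- In the EMC² arm, when the prescriber "attempts to place a new order or change to an existing study medication prescription, an EHR-generated alert will notify the provider" (section 7.1). Then: "When patients leave an encounter, the medication order in Epic will automatically cue printing of both the 1-page, health literate Med Guide Summary".
- Recruitment follows the visit: "Patients will be called via telephone within 1-14 days after their index clinic visit" (section 5.1). Table 1 schedules T1 on days 1-14, and the first portal email on days 3-14.
- Section 7.4: "This is an open-label pragmatic study".
- Section 5.2 nevertheless treats T1 as a baseline: "we will target 330 patients to be recruited and consented to the study, completing the baseline assessment".

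**The concern.** Two things are at stake.

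First, the primary model is not known until the data are in. Two screens choose its covariates, one on imbalance between arms and one on association with the outcome.

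Second, the imbalance screen assumes that T1 precedes treatment, and it does not. For age, sex or education this is harmless, because a visit cannot alter them. CHAI measures motivation and might respond. If EMC² raised CHAI, adjusting for it removes part of the effect under test. If more activated patients were enrolled from EMC² prescribers, failing to adjust leaves bias. If the difference is chance, neither choice biases the estimate on average. The same p-value arises in all three cases, so a reader of the single reported estimate cannot tell what it means.

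**Working it through.** **The plan's own figure.** Inputs from section 10.1: SD 28.4, 150 per arm, 6 per provider, ICC 0.001, 80% power, two-sided 5%. With 50 prescribers (48 df), the detectable difference is 28.4 × (2.011 + 0.849) × √(2/150) × √(1 + 5 × 0.001) = 9.40. At ICC 0.01 it is 9.61. Both agree with the stated 9.4 and 9.6, which are not in dispute.

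**Assumptions not in the documents.** A CHAI difference d of 0.1 or 0.2 SD and a CHAI-knowledge correlation r of 0.2-0.4; T1 screening on 330/2 = 165 per arm; random loss to 150 per arm; a true total effect of 9.4. Only the 10.3.2.2 rule is modeled, since 10.3.3.1 gives no threshold to model.

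**Chance of entry.** The standard error of the CHAI difference is s = √(2/165) = 0.110 SD, so CHAI enters when the observed difference exceeds c = 1.96 × 0.110 = 0.216 SD. The entry probability is P = 1 − Φ((c−d)/s) + Φ((−c−d)/s), which is 15% at d = 0.1 and 44% at d = 0.2.

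**Average estimate under the rule.** Adjusting moves the estimate by 28.4 × r × (observed CHAI difference). Let E be the mean observed difference, counted as zero in trials where CHAI does not enter: E = d·P + s·[φ((c−d)/s) − φ((c+d)/s)].
- d = 0.1: E = 0.1 × 0.149 + 0.110 × (0.230 − 0.007) = 0.039.
- d = 0.2: E = 0.2 × 0.443 + 0.110 × (0.395 − 0.000) = 0.132.

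If EMC² causes the shift (mediation), the rule averages 9.4 − 28.4·r·E. If enrollment causes it (selection), the rule averages 9.4 + 28.4·r·(d − E). A simulation of 20,000 trials per cell agrees with these formulas to within 0.05 point. Its results for r = 0.2, 0.3, 0.4 are:

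| Cause, d | Rule in 10.3.2.2 | CHAI left out | CHAI always in |
|---|---|---|---|
| Mediation, 0.1 | 9.14, 9.03, 8.94 | about 9.4 | not tabulated |
| Mediation, 0.2 | 8.69, 8.32, 7.90 | about 9.4 | 8.29, 7.73, 7.11 |
| Selection, 0.1 | 9.75, 9.92, 10.10 | 9.97, 10.24, 10.55 | 9.40 |
| Selection, 0.2 | 9.78, 9.98, 10.18 | 10.52, 11.10, 11.67 | 9.39-9.40 |

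At 0.2 SD the rule is 0.7-1.5 points low under mediation, with power 74%, 71% and 69%, and 0.4-0.8 high under selection. At 0.1 SD its largest error is 10.10 − 9.40 = 0.7.

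**False positives.** Take no true effect, selection at 0.2 SD and r = 0.4. With CHAI left out, the bias is 28.4 × 0.4 × 0.2 = 2.27 points against a standard error of 28.4 × √(2/150) × √1.005 = 3.29, a ratio of 0.69. A 48-df test then rejects in about 10% of trials. Under the present rule the simulated rate is about 5%.

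**Entry by chance alone.** Table 4 lists about 13 T1 covariates. Treated as independent, the chance that at least one is flagged with no real difference is 1 − 0.95^13 = 49%. This adds no average bias, but it shows how often the model would be decided by noise.

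**The case against.** The strongest reply is that the rule is a reasonable compromise. It is written down in advance, and at 0.2 SD its worst average error (1.5 points) is smaller than that of either fixed choice (2.3 points). Under selection it keeps the false-positive rate near 5%, where leaving CHAI out does not. Selection is also the better documented threat. Post-visit, open-label recruitment from assigned prescribers is in the text, whereas no section says the visit components change CHAI. Section 3.2 does speak of activating patients, but ties this to the portal step. All of this stands, and it rules out presenting the exclusion of CHAI as a plain improvement.

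Two further replies stand only in part. T1 characteristics are already to be compared by arm, but that does not fix the model. Section 6.2 plans to compare participants with refusers, but CHAI is collected only at the T1 interview, so that comparison cannot cover it.

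A reader might also infer that the plan omits prognostic covariates unless they happen to be imbalanced, and so gives up power. The documents do not support this. Section 10.3.3.1 screens on association with knowledge and is a separate way in for prognostic covariates. What can be said against it is that it too is data-driven and has no stated criterion.

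**Conclusion.** The point holds as a matter of prespecification and interpretation, at minor to moderate severity. The order of events and the p < .05 rule are explicit, and the rule cannot separate mediation, selection and chance for CHAI.

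The size rests wholly on assumed values. At a 0.2 SD shift and r of 0.2-0.4, the 10.3.2.2 rule alone gives about 7.9-8.7 points for a true 9.4 under mediation and 9.8-10.2 under selection. At 0.1 SD or less the error is about 0.7 point or less.

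It would be tempting to conclude that EMC² moves CHAI and that the primary result will therefore be diluted. The documents do not show this. They give neither a CHAI effect nor a correlation with knowledge, and even the direction of any error is unknown.

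**What to change.** In 10.3.2.2 and 10.3.3.1, replace both data-driven routes with one covariate list for Aims 1 and 2, fixed before the data are seen:
- the randomization factors, once section 7.3 (workload and site) and section 10.3.1 (role and prescribing volume) are reconciled, and site in any case;
- T1 characteristics the visit cannot plausibly change: age, sex, race/ethnicity, education, income, insurance, number of chronic conditions and health literacy;
- drug type and route of administration, if confirmed to be settled before the alert appears.

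Keep the by-arm T1 table as description only.

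For CHAI, report the primary model with and without it in every case. State in advance which version is primary and why. State also that, if CHAI is higher under EMC², the adjusted estimate is too low under mediation and the unadjusted one too high under selection.

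**Cost.** Wording in two sections and one extra model per outcome; no new data. Adjustment for an unexpected imbalance outside the list is given up. Whichever CHAI version is primary is wrong in one case. Left out, with selection at 0.2 SD and r = 0.4, the estimate is about 2.3 points high and the false-positive rate about 10%, against about 5% under the present rule. Always included, with mediation of the same size, it is up to about 2.3 points low. The gain is that both answers are visible and their directions of error are stated beforehand.
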